4.2.2.1.2 Clinical Laboratory Assessments

Blood and urine samples for determination of clinical chemistry, haematology and urinalysis parameters will be taken at the times detailed in the CSP, and will be assessed in local lab. The parameters outlined in Section 4.3.2 of the CSP, will be collected. Laboratory data will be reported in SI units.

4.2.2.1.3 Vital Signs

Vital signs (temperature, blood pressure, respiration rate, and heart rate measurements) will be collected at screening visit (Day -28 to Day -2), Day -1 and on Day 1 as defined in Table 4 and Table 5 of the CSP. Refer to Table 6 of the CSP for the timings of assessments during the follow-up period.

4.2.2.1.4 ADA

Serum samples for ADA assessments will be conducted utilizing a tiered approach (screen, confirm, titer), and ADA data will be collected at scheduled visits shown in the CSP (Section 4.2.2). ADA result from each sample will be reported as either positive or negative. If the sample is positive, the ADA titer will be reported as well. The impact of ADA on PK, and association with TEAEs and TESAEs will be assessed, if data permit. The number of patients in the as-treated population (defined in Section 3.2) who fulfil the following criteria will be determined. The percentage of ADA-positive patients in each of the category will be calculated, using the number of patients in the as-treated population of the treatment group as the denominator. A patient is defined as being ADA positive if a positive ADA result is available at any time, including baseline and all post-baseline measurements; otherwise ADA negative.

- ADA positive at any visit; the percentage of ADA-positive patients is known as ADA

prevalence.

- The sum of both treatment-induced and treatment-boosted ADA; the percentage of patients fulfilling this criterion is known as ADA incidence.
- ADA positive post-baseline and positive at baseline.
- ADA positive post-baseline and not detected at baseline (treatment-induced ADA).
- ADA not detected post-baseline and positive at baseline.
- Treatment-boosted ADA, defined as a baseline positive ADA titer that was boosted to a 4-fold or higher level (greater than the analytical variance of the assay) following drug administration.
- Persistently positive ADA, defined as having at least 2 post-baseline ADA positive measurements with at least 16 weeks (112 days) between the first and last positive measurement or an ADA positive result at the last available assessment. The category includes patients meeting these criteria who are ADA negative at baseline.
- Transiently positive ADA, defined as having at least one post-baseline ADA positive measurement and not fulfilling the conditions for persistently positive. The category includes patients meeting these criteria who are ADA negative at baseline.
- nAb prevalence, defined as the proportion of nAb positive at any point in time, baseline or post-baseline (remove if not needed)
- anti-YTE prevalence, defined as the proportion of anti-YTE positive at any point in time, baseline or post-baseline (remove if not needed)
- nAb incidence, defined as the proportion of nAb negative at baseline (or ADA negative at baseline) and nAb positive at any post-baseline visits (remove if not needed)
- anti-YTE incidence, defined as the proportion of anti-YTE negative at baseline (or ADA negative at baseline) and anti-YTE positive at any post-baseline visits (remove if not needed)

4.2.2.2 Derivations

Not applicable.

4.2.2.3 Handling of Dropouts and Missing Data

No imputations will be made for any dropouts and missing data.

The imputation for partial start dates of AEs detail, please refer to the Appendix 1.

4.2.2.4 Primary Analysis of Secondary Endpoint

Safety endpoints include:

- Occurrence of all treatment-emergent adverse events (TEAEs), treatment-emergent serious adverse events (TESAEs), adverse events of special interest (AESIs), and new onset chronic diseases (NOCDs).
- Clinical laboratory assessments, vital signs.

ADA endpoints will be summarized as incidence of ADA to nirsevimab in serum.

The primary analysis of secondary endpoints will be summarized by number and percentage for qualitative variables, using the as-treated population. Quantitative variables will be summarized by subjects (n), mean, SD, median, minimum and maximum. Those variables details are described below:

Adverse Events

All AEs will be coded using MedDRA version 23.1 or higher by system organ class and preferred term. Specific AEs will be counted once for each subject for calculating rates but will be presented in total in subject listings. In addition, if the same AE occurs multiple times within a particular subject, the highest severity and level of causality will be reported. AEs will be captured on CRF page “Adverse Event”.

All AEs, both in terms of current MedDRA preferred term and CTCAE grade, will be summarized descriptively by count (n) and percentage (%) for each treatment group. The current MedDRA dictionary will be used for coding. The majority of the AE summaries, unless stated otherwise, will be based on TEAEs. Any AE occurring before study treatment (i.e. before the administration of the first dose on Study Day 1) will be included in the AE listings, but will not be included in the summary tables (unless otherwise stated). These will be referred to as ‘pre-treatment’. However, any AE occurring before the administration of the first dose on Study Day 1 that increases in severity after the first dose will be regarded as treatment emergent and thus will be included in the majority of summary tables.

Treatment-Emergent Adverse Events

All TEAEs will be summarized overall and by MedDRA system organ class and preferred term, severity, and relationship to investigational product.

Severity is classed according to NCI Common Terminology Criteria for Adverse Events (CTCAE) Version 5.0, grade 1-5. Severity will be presented as Grade 1 to 5 (increasing severity), which corresponds to the 5 classes. TEAEs of each severity grade will be summarized by SOC/PT.

If a subject reports the same TEAE more than once within that SOC/ PT, the TEAE with the worst case severity and causally related to the product will be used in the corresponding severity and causally related to the product summaries.

Serious Adverse Events

Serious adverse events (SAEs) are recorded in the “Adverse Events” CRF page with answer “Yes” to question “Serious” and Serious Adverse Event Report page. A summary of SAEs by SOC and PT will be prepared.

Treatment-Emergent Serious Adverse Events

A summary of TESAEs by SOC and PT will be provided.

Presentation

All reported AEs will be listed along with SAE or not indicator, action taken, and outcome of AE, AE start date (study day), AE stop date (study day), duration and investigator's assessment of severity and relationship to study drug.

The following summary tables will be presented:

- any TEAE,
- any IP related (assessed by the investigator) TEAE,

The answer for the question "Relationship, investigational product" as entered into the CRF will be used to identify any IP related TEAE.

In the case that a subject report multiple TEAEs within the same PT, the TEAE with strongest relationship will be used in the corresponding summaries.

- any TEAE with CTCAE grade 3 or higher,

The answer for the question 'AE Severity grade' as entered into the eCRF will be used to identify TEAE of CTCAE grade 3 or higher.

- any IP related TEAE of CTCAE grade 3 or higher,
- any IP related TEAE,

The answer for the question 'Outcome of AE' as entered into the eCRF will be used to identify outcome of TEAE.

- any TESAE,
- any TESAE with outcome fatal,
- any IP related TESAE,

The answer 'Yes' for the question 'Serious' as entered into the eCRF will be used to identify TESAE.

- any TEAE of special interest based on investigator assessment.

Summary information (the number and percent of subjects by system organ class and preferred term separated by treatment group) will be tabulated. If a TEAE condition occurs more than once for a subjects per level of summarization the subjects is only counted once

per MedDRA SOC or PT. SOCs are to be sorted by total decreasing frequency. PTs are to be sorted by total decreasing frequency within each SOC. If SOCs or PTs have the same total frequency they are to be sorted alphabetically.

- Summary of number (%) of subjects who had at least 1 TEAE by PT.
- Summary of number (%) of subjects who had at least 1 TEAE by PT, arranged by SOC.
- Summary of number (%) of subjects who had at least 1 TEAE by PT presented by maximum reported CTCAE grade.
- Summary of number (%) of subjects who had at least 1 TEAE with CTCAE grade 3 or higher by SOC and PT.
- Summary of number (%) of subjects who had at least 1 IP related TEAE by SOC and PT.
- Summary of number (%) of subjects with TESAEs by PT, arranged by SOC. In addition, a data listing of key information for TESAEs will be presented.
- Summary of number (%) of subjects who had at least 1 IP related TESAE by SOC and PT.

Adverse Events of Special Interest

AESIs will be collected from the time of dosing through Day 151 and will be recorded on the “Adverse Events” CRF page with the answer “Yes” to the question “Adverse Events of Special Interest”.

A summary of number (%) of subjects with an AESI will be produced.

- Summary of number (%) of subjects who had at least 1 AESI by PT, arranged by SOC.

New Onset Chronic Disease

NOCDs will be collected from the time of dosing through Day 151 and will be recorded on the “Adverse Events” CRF page with the answer “Yes” to the question “Is this New Onset Chronic Disease?” and the “New Onset Chronic Disease” page.

A summary of number (%) of subjects with an adverse event of NOCD will be produced.

- Summary of number (%) of subjects who had at least 1 NOCD by PT, arranged by SOC.

Skin Reaction

Skin reactions will be collected from the time of dosing through Day 151 and will be recorded on the “Adverse Events” CRF page with the answer “Yes” to the question “Is this Skin Reaction?” and the “Skin Reactions” page.

A summary of number (%) of subjects with skin reaction will be produced.

- Summary of number (%) of subjects who had at least 1 skin reaction by PT, arranged by SOC.

Deaths

If any subjects die during the study, relevant information will be captured on “Serious Adverse Event Report”, “End of Study” and “Statement of Death” CRF pages. All death results will be listed.

Clinical Laboratory, Blood Sample

Frequencies of worst observed Grade 3-4 toxicity, as defined by the National Cancer Institute Common Terminology Criteria for Adverse Events (version 5.0), will be presented for each laboratory parameter by treatment group. Also, laboratory parameters will be assessed by presenting tables containing information related to 2-grade (or greater) laboratory shifts from baseline as well as descriptively over time. Safety of nirsevimab will also be assessed and measured by the summary of serum chemistry and hematology through 150 days postdose.

All laboratory safety data, incorporating serum chemistry and hematology data will be listed for each subject and summarized where appropriate. Serum chemistry and hematology values outside the standard reference ranges will be highlighted in the listings.

Numerical laboratory data (absolute and change from baseline) will be summarised by scheduled study day using standard summary statistics (mean, SD, minimum, Q1, median, Q3, maximum, and number of subjects).

Shift tables for laboratory values by CTCAE 2-grade or greater will be produced. The laboratory parameters for which CTCAE grade shift outputs will be produced are:

- For Haematology, Hemoglobin, Platelets Count, Neutrophils, Lymphocytes and Leukocytes with CTCAE grading will be provided. Eosinophils, Basophils, Monocytes and Hematocrit will not have CTCAE grading.
- For Chemistry, Alanine Aminotransferase, Aspartate Aminotransferase, Alkaline Phosphatas, Creatinine, Total bilirubin, Sodium, Potassium Gamma-Glutamyltransferase, and Glucose with CTCAE grading will be provided. Calcium, Urea will not have CTCAE grading.

For the parameters with no CTCAE grading that are listed in the CSP, shift tables from baseline to worst value on-treatment will be provided.

Clinical Laboratory, Urinalysis

Results from the laboratory will be included in the reporting of this study for urinalysis. A list of laboratory assessments included in the outputs can be found in the protocol section 4.3.2.

Frequencies of worst observed Grade 3-4 toxicity, as defined by the National Cancer Institute Common Terminology Criteria for Adverse Events (version 5.0), will be presented for each laboratory parameter by treatment group. Also, laboratory parameters will be assessed by presenting tables containing information related to 2-grade (or greater) laboratory shifts from baseline as well as descriptively over time. Safety of nirsevimab will also be assessed and measured by the summary of urinalysis through 150 days postdose.

Urinalysis data will be listed for each subject and summarized where appropriate. Urinalysis values outside the standard reference ranges will be highlighted in the listings.

Numerical laboratory data (absolute and change from baseline) will be summarised by scheduled study day using standard summary statistics (mean, SD, minimum, Q1, median, Q3, maximum, and number of subjects).

Shift tables for laboratory values by CTCAE 2-grade or greater will be produced. The laboratory parameters for which CTCAE grade shift outputs will be produced are:

- Protein with CTCAE grading will be provided. pH, Bilirubin, Blood, Specific Gravity, Ketone Bodies (Urine), Color (Urine), Appearance (Urine), RBC/HPF and WBS/HPF will not have CTCAE grading.

Other Laboratory Evaluations

Results from the laboratory will be included in the reporting of this study for pregnancy test and other safety tests. A list of laboratory assessments included in the outputs can be found in the protocol section 4.3.2.

For clinical laboratory assessments, changes in haematology and clinical chemistry variables between baseline and each subsequent on-treatment assessment will be calculated.

Absolute values will be compared to the relevant reference range and classified as low (below range), normal (within range or on limits) or high (above range). Two shift tables will be presented:

- Baseline to highest value post-baseline

- Baseline to lowest value post-baseline

For laboratory values which fall below the lower limit of quantification such that the result is of the form “<xx”, the value will be imputed to be “xx” for the purpose of calculating descriptive statistics in the tables. The original value of “<xx” will still be presented in the listings.

The pregnancy test will be listed subjects whose result is negative or positive.

Vital Signs

The following vital signs measurements will be reported for this study:

Vitals:

- Systolic blood pressure (mmHg)
- Diastolic blood pressure (mmHg)
- Pulse rate (BPM)
- Respiratory Rate (resp/min)
- Temperature (°C)
- Temperature location
 - Oral
 - Tympanic
 - Rectal
 - Axillary
 - Temporal

Vital signs data obtained up until the 151 day safety follow-up visit will be included in the summary tables. Vital sign values and change from baseline (applicable to post baseline measurements) will be summarized by each scheduled time-point. All observed vital signs results will be listed. Worst post-baseline increase is defined as maximum increase compared to baseline, and worst post-baseline decrease is defined as maximum decrease compared to baseline. Both worst changes will be listed as well.

The denominator in vital signs data should include only those subjects with recorded data.

Vital Signs will be presented by treatment group. Systolic and diastolic BP, pulse rate, respiratory rate and temperature will be listed by subject and summarised using standard summary statistics (mean, SD, minimum, Q1, median, Q3, maximum, and number of subjects) for the observed value and change from baseline at each scheduled study visit.

Markedly abnormal quantitative vital signs measurements will be identified in accordance with the following predefined markedly abnormal criteria:

Parameter	Unit	Lower limit	Upper limit
Diastolic blood pressure	mmHg	60	90
Systolic blood pressure	mmHg	90	140
Pulse rate	Beats/min	50	100
Body temperature	Celsius	36.0	37.5
Respiratory rate	Breaths /min	8	20

Pregnancy

Pregnancy information are collected in “Pregnancy Test Urine” and “Pregnancy Report” CRF page and will be listed for as-treated population.

Increased Liver Biochemistry and Evaluation of Hy’s Law

Cases where a subject shows elevations in liver biochemistry may require further evaluation and occurrences of AST or ALT $\geq 3 \times$ ULN together with total bilirubin (TBL) $\geq 2 \times$ ULN may need to be reported as SAEs.

A potential Hy’s Law (PHL) case is defined as aspartate aminotransferase (AST) or alanine aminotransferase (ALT) $\geq 3 \times$ upper limit of normal (ULN) together with total bilirubin (TBL) $\geq 2 \times$ ULN at any point during the study following the start of investigational product irrespective of an increase in alkaline phosphatase (ALP).

A Hy’s Law (HL) case is defined as AST or ALT $\geq 3 \times$ ULN **together with** TBL $\geq 2 \times$ ULN, where no other reason, other than the investigational product, can be found to explain the combination of increases; eg, elevated ALP indicating cholestasis, viral hepatitis, or another drug.

For potential Hy’s Law and Hy’s Law, the elevation in transaminases must precede or be coincident with (ie, on the same day) the elevation in TBL, but there is no specified timeframe within which the elevations in transaminases and TBL must occur. Liver biochemistry data are collected in “Liver Diagnostic Investigations”, “Liver Signs and Symptoms” and “Liver Risk Factors/Life Style Events” CRF page.

Hy’s Law data are collected in “Local Lab Hy's law” CRF page.

Liver related information and Potential Hy’s Law and Hy’s Law will be listed by subjects for as-treated population.

ADA

The incidence of ADA to nirsevimab will be assessed and summarized by number and percentage of subjects who are ADA positive. The impact of ADA on PK, and association with TEAEs and TESAEs will be assessed, if data permit. For ADA summarization details, please refer to 4.2.2.1.4 section.

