3.2 Analysis Populations

Two analysis sets will be considered in this study:

PK Population

The PK population will include all subjects who have received any dose of investigational product (IP), and have at least one measurable postdose serum PK observation and for whom PK blood samples are assumed not to be affected by factors such as important protocol deviations (to be determined prior to unblinding). Pharmacokinetic analyses will be based on the PK population. Subjects who receive placebo will not be part of the PK population.

As-treated Population

All subjects who are randomized into the study and who received any amount of IP will be included in the as-treated population. All safety and ADA summaries will be based on this analysis set and all subjects will be analyzed according to the actual treatment received.

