3.3 General Considerations

Statistical summaries and analyses will be performed by IQVIA under the direction of the Biostatistics Group, AstraZeneca using SAS® Version 9.4 or higher and, where appropriate, additional validated software.

No statistical tests will be conducted in this study. For continuous variables, descriptive statistics will include the number of subjects (n), mean, standard deviation, median, minimum and maximum. When needed, the use of other percentiles (e.g. Q1 and Q3) will be mentioned in the relevant section. Frequencies and percentages will be displayed for categorical data. The denominators for all percentages will be defined as the number of non-missing values for each variable within the analysis set. Percentages will be presented with 1 decimal place. If the original data has N decimal places (if original data has more than 2 decimal places, then N= 2), then the summary statistics except for PK variables should have the following decimal places:

- Minimum and maximum: N
- Mean, median: N + 1
- SD: N + 2

Summaries will be presented within either PK population or as-treated population depending on the endpoint, unless specifically stated otherwise.

Nirsevimab serum concentrations and serum PK parameters will be summarized using descriptive statistics (e.g., n, arithmetic mean, SD, geometric mean, geometric SD, geometric coefficient of variation (CV%) minimum, median, and maximum).

The geometric mean is calculated as the exponential of the arithmetic mean calculated from data on a log scale. The geometric CV% is calculated as $100 \cdot \sqrt{(\exp(s^2) - 1)}$ where s is the SD of the data on a log scale. For T_{\max} only n, median, minimum, and maximum will be reported.

Individual PK concentration versus actual time plots will be presented on linear and semi-log scales. Mean PK concentration versus scheduled sampling time plots will also be presented on linear and semi-log scales.

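### The ADA results paragraph summarizes incidence by a count the SAP elsewhere calls prevalence, and the ADA denominator keeps subjects without evaluable results as non-cases

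*SAP*

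**What the plan says.** Table 5 in SAP section 4.2 gives the incidence of ADA to nirsevimab in serum as the one endpoint for the ADA objective.

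**Definition.** The ADA paragraph of section 4.2.2.4 says: "The incidence of ADA to nirsevimab will be assessed and summarized by number and percentage of subjects who are ADA positive". It then refers to section 4.2.2.1.4 for details. That section says: "A patient is defined as being ADA positive if a positive ADA result is available at any time, including baseline and all post-baseline measurements". Its first category reads "ADA positive at any visit; the percentage of ADA-positive patients is known as ADA", completed on the next line by the word prevalence. Its second category reads: "The sum of both treatment-induced and treatment-boosted ADA; the percentage of patients fulfilling this criterion is known as ADA incidence".

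**Denominator and missing results.** The positivity definition in 4.2.2.1.4 ends "including baseline and all post-baseline measurements; otherwise ADA negative". The percentages are calculated "using the number of patients in the as-treated population of the treatment group as the denominator". Membership of that set needs no ADA sample (section 3.2): "All subjects who are randomized into the study and who received any amount of IP will be included in the as-treated population". The general rule in section 3.3 is different: "The denominators for all percentages will be defined as the number of non-missing values for each variable within the analysis set". Section 4.2.2.3 adds that missing data on the secondary endpoints are not imputed.

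**The concern.** There are two separate issues.

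1. A named endpoint has two readings. If the term ADA positive in 4.2.2.4 carries the meaning given in 4.2.2.1.4, the figure reported as incidence includes subjects who were already positive before dosing and did not change. That is prevalence, and it overstates the response to the product.

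2. A subject without a positive result is negative by default and stays in the denominator. This covers two different situations. A subject with no ADA result at all is counted as ADA negative. A subject with a baseline result but nothing after dosing is counted as not having treatment-induced or treatment-boosted ADA, although that was never observed. Both push the rate down.

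With about 18 and 6 subjects, one reclassified subject visibly changes the percentage that a reader will take away.

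**Working it through.** The SAP states no expected ADA rate, so there is no figure of its own to reproduce. The group sizes come from section 1.3: 24 subjects randomized 3:1 give 24 × 3/4 = 18 on nirsevimab and 24 × 1/4 = 6 on placebo. The counts below are assumptions, because the SAP gives none:

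- t = subjects with treatment-induced or treatment-boosted ADA
- b = subjects positive at baseline and not boosted
- m = subjects not evaluable for incidence (no ADA result, or none after dosing)

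**Weight of one subject.** 1/18 = 5.6 points (nirsevimab); 1/6 = 16.7 points (placebo).

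**Step 1: the two definitions, nirsevimab group, full denominator.** Section 4.2.2.4 read literally gives (t + b)/18. Section 4.2.2.1.4 gives t/18. The gap is b/18, whatever t is.

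| t | b | 4.2.2.4: (t + b)/18 | 4.2.2.1.4: t/18 |
|---|---|---|---|
| 0 | 1 | 1/18 = 5.6% | 0/18 = 0% |
| 1 | 1 | 2/18 = 11.1% | 1/18 = 5.6% |
| 1 | 2 | 3/18 = 16.7% | 1/18 = 5.6% |
| 2 | 1 | 3/18 = 16.7% | 2/18 = 11.1% |

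If b = 0 the two agree.

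**Step 2: the denominator, with incidence as defined in 4.2.2.1.4.** As planned the rate is t/18; among evaluable subjects it is t/(18 − m).

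| t | m | Planned: t/18 | Evaluable: t/(18 − m) | Difference (points) |
|---|---|---|---|---|
| 1 | 1 | 5.6% | 1/17 = 5.9% | 0.3 |
| 2 | 2 | 11.1% | 2/16 = 12.5% | 1.4 |
| 3 | 3 | 16.7% | 3/15 = 20.0% | 3.3 |

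For t and m each from 1 to 3, the first and last rows are the extremes. If m = 0 the difference is zero.

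**Step 3: both together.** With t = 2, b = 1 and m = 2, the same data give 3/18 = 16.7% under 4.2.2.4, 2/18 = 11.1% under 4.2.2.1.4, and 2/16 = 12.5% among evaluable subjects.

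**The case against.** **On the definition.** The ADA paragraph in 4.2.2.4 is a short summary that sends the reader to 4.2.2.1.4, and the amendment history records that section's ADA analysis as updated in version 2.0. There, prevalence and incidence are separate entries. Subjects positive at baseline appear in their own categories, according to whether they are positive after dosing. A programmer who follows the reference would probably produce the right rows, and baseline positives could not be hidden. A reader might infer that the reported incidence will be inflated; the SAP does not support that as a certainty. What stands is that the reference does not say which definition governs. The section it points to also supplies the baseline-inclusive meaning of the very term that 4.2.2.4 uses.

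**On the denominator.** A reader might call this a plain contradiction with section 3.3. It is better read as a specific rule set against a general one, and a specific rule can govern. The all-treated denominator is prespecified and clear. Nor does section 3.3 plainly exclude a subject who has a baseline result but none later, because that subject does have an ADA value. What stands is that the SAP does not declare an exception, and that absence of a result is turned into a negative even though section 4.2.2.3 rules out imputation.

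**On consequences.** A reader might also infer that the misclassification passes into the planned look at ADA against PK and adverse events. That look is conditional on the data permitting it, and the SAP does not say which ADA grouping it will use, so this cannot be shown.

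**Conclusion.** Wrong as written, of moderate weight. The definition conflict is the main part: each baseline-positive subject who is not boosted moves the figure called incidence by 5.6 points (nirsevimab) or 16.7 points (placebo), depending on which section is followed. The denominator is the smaller part: about 0.3 to 3.3 points under the assumed 1 to 3 cases and 1 to 3 unevaluable subjects of 18. Both vanish if no subject is an unboosted baseline positive and every dosed subject has the needed ADA results. The counts are assumptions; the group sizes and both rules are the SAP's own. The endpoint is secondary and all analyses are descriptive, so no test and no sample size depends on it.

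**What to change.** - **Section 4.2.2.4, ADA paragraph:** count subjects *with treatment-induced or treatment-boosted ADA* in place of those who are ADA positive. Keep any-time positivity as prevalence, as 4.2.2.1.4 already does.
- **Section 4.2.2.1.4, classification:** limit ADA negative to subjects with at least one ADA result and no positive one.
- **Section 4.2.2.1.4, denominators:** for prevalence, as-treated subjects with at least one ADA result. For incidence and the categories that compare baseline with post-baseline, as-treated subjects with a baseline and at least one post-baseline result. State that this is the rule for ADA percentages.
- **Presentation:** show numerator and denominator for each percentage, and the number not evaluable in each group.

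The cost is SAP wording and table shells only; the data are already to be collected. Denominators may fall slightly below 18 and 6.
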